5.1 Treatment(s) and Subject Enrollment

The study will be conducted in two geographies, the United States (US) and Europe (EU). Up to 25 US sites (at least 50% of subjects) and up to five EU sites will participate in this study.

At least 510 subjects with ischemic heart disease due to stenotic lesions within coronary arteries that are amenable to treatment with a Resolute Onyx™ 2.0 mm – 5.0 mm stent, meet the eligibility criteria and sign the informed consent form will be included in this study. Subjects may receive treatment of more than one lesion (within a maximum of two target vessels).

The study will have three cohorts with specific and separate analyses (refer to Figure 1). The Primary Cohort will consist of at least 410 subjects who will be treated with at least one 2.0 mm – 4.0 mm diameter Resolute Onyx™ stent. No more than 50 subjects from European sites will be enrolled in the Primary Cohort. A maximum of 41 subjects will be treated with a 2.0 mm Resolute Onyx™ stent.

The Extra Large Vessel (XLV) Cohort will consist of at least 100 subjects who will be treated with at least one 4.5 mm - 5.0 mm diameter stent. Subjects will be enrolled in both the US and EU geographies, with no more than 49 subjects from European sites. Subjects in the XLV Cohort must have at least one lesion amenable to treatment with a 4.5 mm – 5.0 mm stent. Additional lesions may be treated with any available Resolute Onyx™ size stent but these subjects will be designated as a participant in the XLV Cohort as the primary analyses will be based on 4.5 and 5.0 mm stents.

The Bifurcation Cohort will consist of at least 200 subjects of which approximately 15 eligible subjects are expected to be included for analysis from the Primary and XLV cohorts, with an addition of approximately 185 subjects recruited specifically for the Bifurcation Cohort. Subjects will be treated with the full stent size matrix, 2.0 mm – 5.0 mm stents. Subjects will be enrolled in both the US and EU geographies, with no more than 99 subjects from European sites included in the analysis.

RESOLUTE ONYX Post-Approval Study Statistical Analysis Plan

10 October, 2021

Revision 7.0

Page 19 of 32

Form
Medtronic

The study will be conducted to allow data collection and analysis for a minimum of 36 months from treatment of the final subject or until the study has been formally terminated. Health status assessments will be completed at 30 days and 6, 12, 24, and 36 months post-procedure.

Enrollment parameters are included in the study to avoid introduction of bias to the study results due to disproportionate enrollment. Enrollment at any individual site shall not exceed 25% (173 subjects) of the total planned subjects in the study. Enrollment in the US will be >50% of the total enrollment. (refer to Figure 1).

[figure not shown]

Figure 1: Subject Distribution

Subjects will be considered enrolled into the study after they have signed the Informed Consent Form (ICF). Subjects will be considered as participating in the study when the Resolute Onyx™ stent (study stent) is introduced into the guide catheter. The investigator will clearly mark the clinical records to indicate that the subject is participating in this clinical study.

If the study stent is introduced into the guide catheter but not implanted, the subject will be considered part of the Intent-to-Treat population (ITT) and will be followed through the 12-month endpoint and included in the primary analysis of this study. After the 12-month follow up, the subject will exit the study.

If the subject becomes unstable before a study stent is attempted (stent introduced into guide catheter), they will not be treated, a study exit form will be completed, the subject will not be followed, and will not be included in the primary analysis of this study.

5.1.1 Inclusion Criteria

Subject must meet **all** of the following criteria to be eligible for treatment in the trial:

1. Subject age is ≥ 18 years or minimum legal age as required by local regulations
2. Must have symptomatic coronary artery disease; chronic stable angina, silent ischemia, and acute coronary syndromes including non-ST elevation myocardial infarction and ST-elevation myocardial infarction
3. Subject is an acceptable candidate for treatment with a drug eluting stent in accordance with the applicable guidelines on percutaneous coronary interventions, manufacturer's Instructions for Use and the Declaration of Helsinki
4. Subject is willing and able to cooperate with study procedures and required follow up evaluations
5. Subject or legal representative has been informed of the nature of the study and agrees to its provisions and has provided an Institutional Review Board (IRB)/ Ethics Committee (EC) approved written informed consent, including data privacy authorization
6. Female subjects of childbearing potential must have a negative pregnancy test within 7 days before the study procedure
7. Subject requires treatment of one or more target lesion(s) amenable to treatment with a Resolute Onyx™ 2.0 mm – 5.0 mm stent in up to two separate target vessels

In addition to the general inclusion criteria listed above, subjects must meet all of the following criteria to be eligible for treatment in the Bifurcation Cohort:

1. The subject requires treatment of a single de novo bifurcated lesion amenable to treatment with provisional stenting technique
 - a. All Medina classification types
 - b. De novo lesion in native coronary artery
 - c. Main branch $\geq 2.25 - 5.0$ mm
 - d. Side branch ≥ 2.0 mm
 - e. Lesion length ≤ 35 mm
2. Target lesion(s) must have a stenosis of $\geq 50\%$ and $< 100\%$
3. Target vessel(s) must have a Thrombolysis In Myocardial Infarction (TIMI) flow ≥ 2

5.1.2 Exclusion Criteria

Subjects will be excluded from the trial if **any** of the following criteria are met:

1. Known hypersensitivity or contraindication to aspirin, heparin and bivalirudin, thienopyridines, cobalt, nickel, platinum, iridium, chromium, molybdenum, polymer coatings (e.g. BioLinx™), anticoagulations or a sensitivity to contrast media, which cannot be adequately pre-medicated
2. History of an allergic reaction or significant sensitivity to drugs such as zotarolimus, rapamycin, tacrolimus, everolimus, or any other analogue or derivative

RESOLUTE ONYX Post-Approval Study Statistical Analysis Plan

10 October, 2021

Revision 7.0

Page 21 of 32

Form

Medtronic

3. Subjects who are judged to have a lesion that prevents complete inflation of an angioplasty balloon or proper placement of the stent or stent delivery system
4. Unprotected left main coronary artery disease (no patent bypass graft(s) to one or more branches of the left coronary artery; the left anterior descending or circumflex artery, with an obstruction greater than 50% in the left main coronary artery)
5. Subjects with planned PCI of three vessel disease (includes staged procedures)
6. Currently participating in an investigational drug or another device study that has not completed the primary endpoint or that clinically interferes with the current study endpoints
Note: Studies requiring extended follow-up for products that were investigational, but have since become commercially available, are not considered investigational studies.
7. Planned surgery that would cause interruption in recommended DAPT duration per current

In addition to the general exclusion criteria listed above, subjects will be excluded from the Bifurcation Cohort if **any** of the following criteria are met:

1. Planned two stent technique (main branch and side branch) of a bifurcation
2. Subjects with more than one bifurcation lesion
3. Trifurcation lesions
4. Planned treatment of any additional lesion(s) in the bifurcation target vessel(s), inclusive of branches within 12 months
5. Target lesion(s) are located in native vessel(s) within 5 mm distal to anastomosis with a bypass graft (including but not limited to saphenous vein graft or a left/right internal mammary artery (LIMA/RIMA)) and/or with more than 40% diameter stenosis anywhere within the graft
6. Impaired renal function (serum creatinine >2.5 mg/dl or 221 μ mol/l) or on dialysis
7. Left ventricular ejection fraction (LVEF) \leq 30%

6. Determination of Sample Size

The primary endpoint for all subjects participating in the Primary and XLV Cohorts in this study is Target Lesion Failure (TLF), defined as cardiac death, target vessel myocardial infarction (Q wave and non-Q wave), or clinically driven target lesion revascularization (TLR) by percutaneous or surgical methods, at 12 months.

The primary endpoint for subjects participating in the Bifurcation Cohort is Target Vessel Failure (TVF) at 12 months.

The following secondary endpoints will be assessed for all subjects at hospital discharge, 30 days and 6, 12, 24, and 36 months post-procedure.

1. Acute Success (Device, Lesion, Procedure)
2. Cardiac Death
3. Target Vessel Myocardial Infarction (TVMI)
4. Target Lesion Revascularization (TLR)
5. Target Vessel Revascularization (TVR)
6. Cardiac Death and TVMI
7. Major Adverse Cardiac Event (MACE)
8. Target Lesion Failure (TLF)
9. Target Vessel Failure (TVF)
10. Stent Thrombosis (ST)

6.1 Primary Cohort

If the 12-month TLF rate of the Resolute Onyx stent™ is shown to be significantly less than 17.5%, then the Primary Cohort will be considered to have met its primary endpoint. In other words, the null and the alternative hypotheses are:

$$H_0: P_{TLF} \geq 17.5\%$$

$$H_1: P_{TLF} < 17.5\%$$

where P_{TLF} is the true primary endpoint rate for the study stent. Rejection of the null hypothesis will signify that the PG is met.

Assuming a one-sided alpha level of 0.05 and a true event rate of 11.3%, an effective sample size of 369 subjects will yield 96% power to reject the null hypothesis. Assuming a 10% loss to follow-up rate, a total sample size of 410 RESOLUTE ONYX Post-Approval Study subjects will be enrolled in the Primary Cohort. An expected event rate of 7.95% was derived from both arms of the RESOLUTE All-Comers (RAC) trial (excluding unprotected left main (UPLM) and PCI of 3 vessels). Modification of 3.31% was added to the expected rate to adjust the difference in MI reporting per third UDMI. This resulted in the expected event rate of 11.3%. The performance goal 17.5% is a 55% extension from the expected event rate of 11.3%.

6.2 XLV Cohort

One hundred subjects will be treated with 4.5 mm or 5.0 mm stents and enrolled in the XLV Cohort. There is no formal hypothesis for the XLV Cohort, and descriptive statistics will be provided.

6.3 Bifurcation Cohort

If the 12-month TVF rate is shown to be significantly less than 24.5% for the RESOLUTE ONYX Bifurcation Cohort, then the Bifurcation Cohort will be considered to have met its primary endpoint. Therefore, the null and the alternative hypotheses are:

$$H_0: P_{TVF} \geq 24.5\%;$$

$$H_a: P_{TVF} < 24.5\%$$

where P_{TVF} is the true primary endpoint rate for the study stent. Rejection of the null hypothesis will signify that the PG is met. This PG is based on review of clinical evidence from published literature.

Assuming a one-side alpha level of 0.05 and a true event rate of 16.3%, an effective sample size of 180 subjects will yield 85% power to reject the null hypothesis. Assuming 10% loss to follow-up rate, a total sample size of 200 subjects will be needed; hence data on a total of 200 subjects will be generated.

The expected rate for the RESOLUTE ONYX Bifurcation Cohort was obtained by utilizing the weighted average of outcomes from the RESOLUTE All-Comers (RAC) study in patients with single bifurcations treated with single or double stents (excluding unprotected left main lesions and patients with three vessel disease), and the from the provisional stenting arm of the TRYTON study. The weighted average is shown in Table 1. Then the expected rate of 12-month TVF was modified upwards by 3.3% in order to account for the utilization of Third UDMI definition. Therefore, the expected rate of 12-month TVF is 16.3%.

Table 1: Expected 12-month TVF rate for the RESOLUTE ONYX Bifurcation Cohort

Study/Arm	Stent Used	N	12m TVF Rate
RAC (Resolute Arm) - single bifurcation treatment	ZES	133	11.60%
RAC (Xience V Arm) - single bifurcation treatment	EES	136	12.20%
TRYTON – Provisional Stenting Arm*	DES	339	13.9%**
Weighted Average			13.00%
* Data from TRYTON SSED			
**Adjusted downwards from 15.3% to 13.9% to account for the difference in true versus non-true bifurcated lesions per Medina Classification that were treated in the Resolute All comer study and the provisional stenting arm of the TRYTON study			

7. Statistical Methods

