7.1.4 Pooling of Bifurcation Cohort and bifurcated lesions from Primary/XLV Cohorts

It is intended to pool the two cohorts (Bifurcation Cohort and bifurcation subset from Primary/XLV cohorts). Comparability between the two cohorts on baseline characteristics and on the primary endpoint will be assessed.

- **Covariate homogeneity**

The first step will be to assess the homogeneity of the covariates between two cohort populations. The two-sample t-test or Fisher's exact test will be used depending on the distributions of the covariates. The covariates that will be considered include: lesion length, baseline RVD, age, sex, diabetes, history of MI and worst Canadian Cardiovascular Society angina class. Statistical non-significance (significance level set at 0.15) for any of the covariates is supportive evidence of the comparability of the cohorts without adjusting for that covariate. However, any covariate for which the group difference is deemed to be clinically and statistically significant could be adjusted by using propensity scores as discussed below to account for any covariate imbalances.

- **Outcome Comparability**

If any of the above baseline covariates is significantly different, then the outcome of 12 months TVF rate between the two cohorts will be compared as the following: for each individual a propensity score will be calculated using logistic regression, with indicator for cohort (Bifurcation cohort, bifurcation subset from Primary/XLV cohorts) membership as the dependent variable and the above mentioned covariates as the independent variables (covariates will be included regardless of whether or not they are deemed homogenous). Patients will then be categorized into quintiles based on this propensity score. The 85% confidence interval of propensity score quintile adjusted difference between cohorts in TVF at 12 months will be calculated. If the 85% confidence interval contains zero (0), then the two cohorts will be considered poolable.

If the two cohorts are deemed suitable for pooling based on this analysis, then combined data from the two cohorts will be used to compared to the performance goal. If the data from the two cohorts are not poolable, then Medtronic will discuss with FDA on the next steps.

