7.9.1.3 Bifurcation Cohort

The count and percentage of subjects with 12-month TVF will be provided. A one-sided upper bound of the 95% CI of the observed 12-month TVF rate will be calculated through binomial (exact) method. If this upper limit of the 95% CI is below 24.5%, the clinical objective will be considered to have been met for the Bifurcation Cohort.

As a supplementary analysis, to account for missing data, subjects who drop out prior to 330 days post-procedure and do not experience TVF will have their 12-month TVF-missing status ("yes"/"no") imputed using the multiple imputation and tipping point analysis.

The multiple imputation approach will use SAS V9 PROC MI. The covariates to be used in the imputation model are lesion-length, baseline RVD, age, sex, diabetes, history of MI, Canadian Cardiovascular Society Angina Class, and TVF status at visits prior to dropout. One hundred imputed data sets will be generated. An overall TVF rate and its one-sided upper 95% confidence intervals will be generated across the one hundred imputed data sets. For the subjects with 2 or more target lesions, the longest lesion length and the smallest baseline RVD will be used in the imputation model.

The tipping point analysis will impute the most 12-month TVF-missing status as “yes” so that the one-side upper 95% confidence interval will be less than or equal to the performance goal of 24.5%. For all the three cohorts, the analysis of the primary endpoint will be repeated for PP set as a secondary analysis.

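### Medina lesion type is built into the Bifurcation Cohort's expected rate, goal and power, but is left out of the imputation model, the pooling check and any comparison with the goal

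*SAP*

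**What the plan says.** SAP 6.3 (Table 1) and Protocol 14.2.3 (Table 8) build the expected TVF rate from two arms of an all-comers study and the provisional-stenting arm of a dedicated bifurcation trial. The last of these carries the footnote "Adjusted downwards from 15.3% to 13.9% to account for the difference in true versus non-true bifurcated lesions per Medina Classification". SAP 6.3 then adds 3.3 points for the Third Universal Definition of MI. Protocol 14.2.3 sets the goal 50% above the result.

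The sample size rests on that rate: "Assuming a one-side alpha level of 0.05 and a true event rate of 16.3" per cent, "an effective sample size of 180 subjects will yield 85% power to reject the null hypothesis". Allowing for loss, "Assuming 10% loss to follow-up rate, a total sample size of 200 subjects will be needed".

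Eligibility (SAP 5.1.1, Protocol 9.3) takes "All Medina classification types", with no quota by type. The decision rule in SAP 7.9.1.3 is an unadjusted exact binomial bound: "If this upper limit of the 95% CI is below 24.5%, the clinical objective will be considered to have been met for the Bifurcation Cohort".

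Two covariate lists matter here:
- TVF multiple imputation, SAP 7.9.1.3: "lesion-length, baseline RVD, age, sex, diabetes, history of MI, Canadian Cardiovascular Society Angina Class, and TVF status at visits prior to dropout".
- Comparability of the recruited cohort with the bifurcation subset of the Primary and XLV Cohorts, SAP 7.1.4: "lesion length, baseline RVD, age, sex, diabetes, history of MI and worst Canadian Cardiovascular Society angina class".

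Neither contains Medina status, nor do the site and region checks in SAP 7.3. Medina status does appear in a true versus non-true subgroup (SAP 7.9.3) and a descriptive analysis of true bifurcations (SAP 7.9.4, Protocol 14.5.1).

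**The concern.** A single-arm comparison with a fixed goal has no concurrent control to absorb differences in case mix. By adjusting one source rate for lesion type, the plan accepts that lesion type shifts TVF, so the goal and power refer to some particular true/non-true mix. The documents do not give that mix, the rates by lesion type, or the step from 15.3% to 13.9%. Once the cohort is enrolled, a reader can see its mix but cannot tell whether it is milder or harder than the one assumed.

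The same factor is also absent from two places where a known predictor of the outcome would normally be included: the model that fills in missing TVF, and the check on whether two groups of subjects may be pooled. What is at stake is how to read a result near the limit, and whether the stated power applies to the cohort actually enrolled.

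**Working it through.** **Inputs.** From SAP 6.3: source rates 11.6% (N=133), 12.2% (N=136) and 13.9% (N=339; 15.3% before adjustment); uplift 3.3 points; one-sided alpha 0.05; 180 evaluable; 10% loss. From Protocol 14.2.3: 50% margin. From SAP 7.9.1.3: exact one-sided 95% upper bound below 24.5%.

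**1. The plan's own figures reproduce.**
- Weighted rate: (133×11.6 + 136×12.2 + 339×13.9)/608 = 13.02%.
- Expected rate: 13.0 + 3.3 = 16.3%.
- Goal: 1.5 × 16.3 = 24.45%, rounded to 24.5%.
- Total: 180/0.90 = 200.
- Pass limit at n=180: 34 events give an exact upper bound of 24.34% and 35 give 24.94%, so the cohort passes with 34 events or fewer.
- Type I error: P(X ≤ 34 | 24.5%) = 4.5%.
- Power: P(X ≤ 34 | 16.3%) = 85.1%, against the stated 85%.

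**2. Adjustment removed from the table.** (133×11.6 + 136×12.2 + 339×15.3)/608 = 13.80%; adding 3.3 gives 17.1%, a rise of 0.8 point.

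**3. Unadjusted dedicated-trial rate.** 15.3 + 3.3 = 18.6%. The adjusted rate on the same scale is 13.9 + 3.3 = 17.2%. Of the 2.3 points between 16.3% and 18.6%, the footnote therefore attributes 1.4 to Medina mix (18.6 − 17.2). The other 0.9 (17.2 − 16.3) remains after that adjustment.

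**4. The footnote's 1.4-point step applied to the planned rate.** This assumes the step carries over to the whole cohort: 16.3 + 1.4 = 17.7% for a harder mix, 16.3 − 1.4 = 14.9% for a milder one.

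**5. Effect at n=180, goal fixed at 24.5%.**

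| True TVF | Scenario | Expected events | P(pass) |
|---|---|---|---|
| 14.9% | one step milder (assumed) | 26.8 | 94.2% |
| 16.3% | as planned | 29.3 | 85.1% |
| 17.1% | adjustment removed | 30.8 | 77.2% |
| 17.7% | one step harder (assumed) | 31.9 | 70.2% |
| 18.6% | unadjusted dedicated-trial rate | 33.5 | 58.5% |

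Power falls below 80% once the true rate exceeds 16.8%, and below 50% above 19.2%.

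**6. Larger swings need shares the documents do not give.** Suppose 80–100% of the dedicated trial's lesions and 40–70% of the all-comers lesions were true bifurcations. A cohort made up wholly of true bifurcations would then have TVF of 18.6–21.4% and power from 58% down to 24%. A cohort with none would have power from 85% up to about 100%. These are assumed shares with extreme mixes.

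**7. Reach of the two covariate lists.** At 10% loss, imputation concerns about 200 × 0.10 = 20 subjects and is supplementary. The pooling check concerns a subset of about 15 (SAP 5.1).

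**The case against.** The strongest reply is that an unadjusted comparison with a fixed goal, in a cohort open to every Medina type, is a legitimate design. Lesion type is already reported by subgroup, so the mix and the rates by type will be visible. The omissions from the imputation and pooling lists touch few subjects and do not enter the primary bound. All of this stands, and it is why the primary test needs no change. What the descriptive tables cannot do is relate the observed mix to the one behind 24.5%, because that share is not stated.

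Two stronger readings are tempting, and the documents support neither.

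- *Case mix alone decides pass or fail.* On the documents' figures the expected count rises from 29.3 to between 30.8 and 33.5, still within the limit of 34. The upper figure may also include differences between the source studies that have nothing to do with Medina type.
- *A milder mix inflates the false-positive rate.* That requires a goal that slides with the mix. The stated null is a fixed 24.5%. Any true rate below it lies in the alternative, so passing there is a correct rejection, and the error rate at 24.5% remains 4.5%.

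Nor do the documents show how strongly Medina type predicts TVF. They apply an adjustment without giving rates by type.

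**Conclusion.** The point holds as a modest, low-cost improvement. The plan treats true versus non-true status as prognostic when it derives the goal, then uses it only descriptively. Relative to the planned 85.1%, power is 77.2% with the adjustment removed and 58.5% at the unadjusted dedicated-trial rate. In expected events that is about 1 to 4 more out of 180, enough to tip a close result and no more than that.

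These figures assume exactly 180 evaluable subjects, the exact rule as written, and the 3.3-point uplift applying equally to every scenario. The arithmetic behind the 24.5% goal and the 85% power is correct.

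**What to change.** 1. **SAP 6.3:** state the true/non-true share behind the 13.9%, how 15.3% became 13.9%, and whether true was defined as in SAP 7.9.3 (111, 101, 011).
2. **SAP 7.9.1.3, imputation:** add Medina true/non-true status to the TVF imputation covariates, and name the reading used (site or core laboratory), since the documents do not say who assigns it.
3. **SAP 7.1.4:** add the same indicator to the comparability covariates.
4. **SAP 7.9.1.3, one supplementary analysis:** 12-month TVF directly standardised to the share in item 1, that is w × (true rate) + (1 − w) × (non-true rate), with w the assumed true share. Name the one-sided 95% upper-bound method for a weighted sum of two binomial proportions, for example MOVER with Wilson limits in each stratum, and report it beside 24.5%. If w is known only as a range, show the result across it. The cohort allows one bifurcation lesion per subject, so each subject falls in a single stratum.

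Keep the exact primary test and the 24.5% goal.

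**Cost:** SAP wording and one more table; the planned subgroup already needs Medina class. The standardised rate will have a slightly wider bound. The pooling model gains an eighth covariate although one group has only about 15 subjects, so its estimates will be less stable.
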